At the 2 year time point all subjects will have a 7444 mg egg white protein desensitization OFC on therapy. If the subject fails the 7444 mg egg white protein OFC on therapy, the subject will stop therapy and treatment options will be discussed with the subject. If the 7444 mg egg white protein OFC on therapy is passed, then the subject will be removed from therapy for 8-10 weeks and tested for sustained unresponsiveness with a second 7444 mg egg white protein OFC. If this 7444 mg egg white protein OFC off therapy is passed with successful consumption of an open feeding of egg, the subject will be considered to have achieved sustained unresponsiveness and advised to add egg to their diet on a regular basis and will be followed at 3 months by phone and 6 months in clinic to assess their egg diet history and reactivity to egg. If the subject fails the 7444 mg egg white protein OFC off therapy, further treatment options will be discussed with the subject.

ANNUAL LONG TERM FOLLOW-UP

All subjects will be contacted by telephone at years 3, 4, and 5 (through September 30, 2018) to assess consumption of egg in the diet.

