4.3 Premature Subject Termination from the Study

4.3.1 Criteria

No subject initiating therapy in this trial will be replaced.

Any subject may be prematurely terminated from additional allergen exposures, but maintained on longitudinal follow-up for the following reasons:

• Anaphylaxis resulting in hypotension, neurological compromise or mechanical ventilation secondary to Baked Egg or Egg OIT dosing or any egg food challenge.

Any subject deemed to have severe symptoms and receives aggressive therapy at any time should be discontinued from further therapy, including the following:

- Poor control or persistent activation of secondary atopic disease (e.g., AD, asthma).
- Started on ARBs, ACE inhibitors, beta-blockers, or other prohibited meds and there are no alternative meds available per the prescribing doctor, they will be removed from further treatment.
- Pregnancy.
- Egg OIT Group subjects:
 - Circumstances (e.g., concurrent illness, such as gastroenteritis) requiring missed Egg OIT maintenance dosing of >7 consecutive days (this does not include subjects intentionally removed from therapy to administer an OFC off therapy).
 - Non-adherence with home Egg OIT dosing protocol (excessive missed days; i.e., >3 consecutive days missed on 3 occasions), would be a safety issue warranting discontinuation.

Any subject may be prematurely terminated from the study if:

- The subject elects to withdraw consent from all future study activities, including followup.
- The subject is "lost to follow-up" (i.e., no further follow-up is possible because attempts to reestablish contact with the subject have failed).
- The subject has biopsy documented Eosinophilic Esophagitis (EoE).

• The subject dies.

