* Mechanistic blood draw may not to exceed 50 cc in a day (but no more than 5 cc/kg in 24 hrs or 9.5 cc/kg in 8 weeks).

Egg OIT Treatment Overview:

Egg OIT administration will include an initial escalation day (Visit 01) with egg oral immunotherapy dosing beginning at 0.1 mg egg white solid with graduated doses up to 25 mg (if tolerated) occurring in the Clinical Research Center or appropriate monitored clinic setting. The Egg OIT assignment group (that failed the baked egg challenge) will only escalate to 12 mg egg white solid maximum on Day 1. This will be followed by Egg OIT escalation every 2 weeks in the Clinical Research Center or monitored clinic setting. Subjects at the end of Day 1 tolerating less than 3 mg single dose will be considered an initial day escalation desensitization failure and followed longitudinally.

Following attainment of daily dosing of the maximum tolerated dose (range 350 mg egg white solid to a target of 2500 mg), a maintenance period for at least 8 weeks followed by a 7444 mg egg white protein OFC will occur at 1 year (Visit 04).

All subjects who did not reach a 2500 mg egg white solid maintenance dose will resume build-up starting at their current maintenance dose and stopping at a maximum 2500 mg maintenance dose, or earlier if symptoms prevent further build-up. The doses administered and parameters for build-up in the post 7444 mg egg white protein OFC phase will be identical to those in build-up prior to the 7444 mg egg white protein OFC.

With each escalation, phone contact will occur after the first week on home dosing to assess symptoms and compliance. A targeted history and physical exam will be performed at each visit. Subjects will be assessed for exacerbation of atopic dermatitis or asthma (as determined by active wheezing) prior to each in clinic dosing.

In addition to dosing visits, subjects will return to the Clinical Research Center at 3 months (Visit 02), 6 months (Visit 03), 16 months (Visit 05) and 20 months (Visit 06) for mechanistic blood draws. A medical and diet history, and physical exam will also be performed at these visits.

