If a subject fails dose escalation after three consecutive (with 2-4 weeks between) attempts, he/she will be considered a dose escalation failure and the last tolerated dose will be accepted as the maintenance dose. For a completed dose escalation with no symptoms, subjects should be observed for 30 minutes. For mild symptoms, subjects should have a 1-2 hours post-protocol observation period. For moderate to severe symptoms, the observation period should be at least 4 hours and up to 24 hours based on symptoms and treatment regimen needed to stabilize the subject.

Any subject deemed to have severe symptoms including hypoxia, hypotension or change in mental status (stage 3 defined in Appendix 3) and receives aggressive therapy at any time should be discussed with the Study Chair or Co-Chair and discontinued from active therapy.

For specific questions related to dosing escalation or continuation of the same dose that are not answered in the above protocol, the Study Chair or Co-Chair will be available for questions and decision-making.

Any subject who discontinues build-up dosing due to repeated allergic reactions to the egg product will have his/her mechanistic blood drawn within approximately 1 week of discontinuation of therapy.

6.4.2 Treatment for reactions during the Build-Up and Maintenance Phases

Treatment of individual reactions should be with either an antihistamine and/or epinephrine, along with IV fluids, albuterol, and steroids as indicated. Generally, for mild and moderate symptoms, the subject should receive antihistamines, and for more severe symptoms, the subjects should receive epinephrine, antihistamines, and then the other medications as indicated. If severe anaphylaxis (stage 3 defined in Appendix 3) occurs at any time, dose escalation will stop and the dose will be reduced to the last tolerated dose (must be at least 350 mg egg white solid) and the subject continued on that dose as long-term maintenance without further escalation.

Antihistamines

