If a subject receives antihistamines only, the dose escalation can be continued. If symptoms during a build up day require antihistamines in multiple doses or in combination with other medications (except epinephrine), there should be a dose reduction by 1-2 doses with the next dose given in the CRC. If dose escalation fails or requires treatment after 2 more escalation attempts each spaced 2 to 4 weeks apart, the dose should be reduced to the last tolerated dose (must be at least 350 mg egg white solid to continue) and continued long term without further escalation.

Epinephrine

Any reaction (in clinic or at home) that requires 2 or more doses of epinephrine counts towards the stopping rules for the protocol. Further dose escalation would not occur in this individual and maintenance on the last tolerated dose (must be greater than 350 mg) would be maintained.

Clinic

If a single administration of epinephrine is required during in clinic escalation, the dose should be reduced by 2 doses, and the subject continued on that dose for 4 weeks. After 4 weeks at the reduced dose, an escalation attempt may be tried in clinic.

If a single administration of epinephrine is required a second consecutive time during this escalation attempt, the dose should be reduced by 2 doses, and the subject continues on that dose for 6-8 weeks. After 6-8 weeks at the reduced dose, an escalation attempt may be tried in clinic.

If a single administration of epinephrine is required a third consecutive time during this escalation attempt, the dose should be reduced by 2 doses (if the reduced dose is at least 350 mg egg white solid) and the subject continued on that dose as long-term maintenance without further escalation.

Home

If a single administration of epinephrine use occurs during dosing at home, this epinephrine use is not counted as one of the uses described above, unless severe anaphylaxis occurs at home. The subject should return to clinic for an observed dose prior to resuming any dosing at home. The investigator may or may not decide to dose reduce depending on the specific circumstances surrounding the reaction.

MAINTENANCE PHASE (PRE 1 YEAR 7444 MG EGG WHITE PROTEIN OFC PHASE)

This phase consists of the subject receiving the maximum achieved daily dose of either baked egg or egg white solid OIT (as described above) for at least 8 weeks at home. The subject will continue to follow an egg-restricted diet for the duration of the study.

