For any noted symptoms during the maintenance phase, the same general study dosing rules for the build-up phase will be followed. Dosing reductions during the maintenance phase will be determined by the investigator based on the circumstances surrounding the reaction and subsequent dosing reactions.

Both Treatment Groups:

One year 7444 mg egg white protein OFC (at the conclusion of the initial build-up and initial maintenance phase) - All subjects will undergo a 7444 mg egg white protein OFC at 52 weeks after reaching the maximum achieved daily dose for 8 weeks as described above. Even though subjects initially may not tolerate more than approximately 2 gm of baked egg protein or 350 mg of egg white solid, long-term administration of egg may result in the capacity to tolerate much higher doses, and indeed 80% of individuals on 300 mg of egg white solid maintenance therapy for 24 months were "protected" and passed a 10 gm OFC.³⁷

All subjects who did not reach the maximum maintenance dose of Egg OIT will resume build-up starting at their current maintenance dose and stopping at the maximum maintenance dose or earlier if symptoms prevent further build-up. The doses administered and parameters for build-up

in the post 1 year 7444 mg egg white protein OFC phase will be identical to those in build-up prior to the 1 year 7444 mg egg white protein OFC.

Long Term Maintenance:

The year 2 maintenance portion of the study is to determine if the Baked Egg and/or Egg OIT can induce the development of sustained unresponsiveness to egg. Subjects in the treatment arm will remain on a daily dose of Baked Egg or Egg OIT (or resume build-up to reach the maximum maintenance dose as described above at least 4 weeks prior to the 2 year 7444 mg egg white protein OFC).

Subjects on each arm of the study will be followed with visits at 4 months (Visit 05) and 8 months (Visit 06) after the 1 year 7444 mg egg white protein OFC. At these visits, serum for egg-specific IgE and IgG4 will be obtained (up to 10 mL). Subjects will be called monthly to assess for dosing compliance, symptoms and a targeted history.

Missed Baked Egg Doses:

Baked Egg subjects will be encouraged to take the daily baked egg dose. Missed doses will be monitored for compliance through daily dosing diaries.

Missed Egg OIT Doses at any Phase of the Study:

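### The year-2 build-up text makes no exception for Egg OIT children whom Section 6.4.2 bars from further escalation below 2500 mg, and the protocol does not say which rule governs

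*Protocol*

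**What the plan says.** **The bars.** Protocol Section 6.4.2 covers reactions during both build-up and maintenance of Egg OIT. It ends escalation in these cases:

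- A reaction, in clinic or at home, needs two or more doses of epinephrine: "Further dose escalation would not occur in this individual". The held dose must be above 350 mg.
- Epinephrine is needed a third consecutive time at in-clinic escalation. The dose drops two steps, to no less than 350 mg, with "the subject continued on that dose as long-term maintenance without further escalation".
- Build-up symptoms need repeated antihistamine doses or a combination of medications (epinephrine excepted), and two further attempts also fail or need treatment. The child goes back to the last tolerated dose, at least 350 mg, "and continued long term without further escalation".
- Stage 3 anaphylaxis: "If severe anaphylaxis (stage 3 defined in Appendix 3) occurs at any time, dose escalation will stop", again with long-term maintenance at a held dose. Elsewhere such children leave treatment. The build-up symptom algorithm in Section 6.4 says they "should be discussed with the Study Chair or Co-Chair and discontinued from active therapy", and Section 4.3.1 says "Any subject deemed to have severe symptoms and receives aggressive therapy at any time should be discontinued from further therapy". This bar therefore matters only for a child who is not discontinued.

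**The year-2 instructions.** The Egg OIT Treatment Overview in Section 6.4 says "All subjects who did not reach a 2500 mg egg white solid maintenance dose will resume build-up starting at their current maintenance dose". That sentence goes on to say that build-up stops at 2500 mg, or sooner if symptoms prevent it from going further. The paragraph on the 1-year challenge under Both Treatment Groups says "All subjects who did not reach the maximum maintenance dose of Egg OIT will resume build-up". Section 3 (after the Egg OIT dosing table) and SAP Section 4.1 say that children below 2500 mg will be escalated if they tolerate it. The Section 6.4 text on build-up after the 1-year challenge starts subjects on the dosing scheme again until 2500 mg. Footnote 5 of Appendix 1.A says only that they may escalate.

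**The concern.** A child barred in year 1 before reaching 2500 mg is covered by both sets of instructions. Section 6.4.2 says not to escalate, with no end date. The year-2 text, read literally, restarts escalation.

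The rule protects children who have already needed repeated epinephrine or repeated multi-drug treatment. Two sites could treat the same child differently, and each could cite the protocol. The Study Chair is available for dosing questions that the protocol leaves unanswered. Here it appears to give an answer in each place, so a site that reads only one of them may see nothing to ask.

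**Working it through.** The plan gives no figure on this point. The check sets the passages side by side, with one small calculation to see whether the conflict can arise in practice.

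**1. Who is covered by both rules.** The bars apply to any Egg OIT child who meets the trigger. The year-2 text applies to every Egg OIT child who has not reached 2500 mg. A child who meets a trigger in year 1 below 2500 mg is in both groups.

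**2. Whether the year-2 qualifiers exclude that child.** The two qualifiers are tolerance (Section 3, SAP Section 4.1) and stopping sooner because of symptoms (Section 6.4). Both limit how far a resumed build-up goes, and both are tested by escalating, which is what the bar forbids. Neither says who must not resume. None of the year-2 passages refers to Section 6.4.2.

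**3. Whether there is time for it to happen.** Inputs from the Section 3 dosing table and Appendix 1.A: 350 mg is dose 16, 2500 mg is dose 25, steps are 2 weeks apart, and the on-therapy challenges are at weeks 52 and 104. Section 6.4 adds a 4-week hold before the second.

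- Time needed from 350 mg: (25 − 16) × 2 = 18 weeks.
- Under the two-epinephrine bar the dose must exceed 350 mg, so the lowest table dose is 450 mg (dose 17): (25 − 17) × 2 = 16 weeks.
- Time available: 104 − 4 − 52 = 48 weeks.

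A full climb fits within year 2. From the lowest held dose it is a rise of 2500 / 350 ≈ 7.1 times.

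**4. Whether year-1 halts generally survive the 1-year challenge.** They do not. Section 6.4 stops the first build-up at 44 weeks and holds the dose for 8 weeks. Those children are then meant to resume. The pre-1-year text also halts escalation after three unsuccessful attempts and carries the dose forward as maintenance, without calling the halt permanent. On the year-2 wording those children restart as well. So the fact that escalation stopped in year 1 does not tell a site whether it stays stopped.

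**5. Cross-references.** The initial-escalation text in Section 6.4 and footnote 3 of Appendix 1.A send the reader to Section 6.4.1 for epinephrine delays. Section 6.4.1 deals with reactions to Baked Egg. The Egg OIT rules are in 6.4.2. This is a clerical error, and the point does not depend on it.

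**The case against.** The best reply is that the specific safety rule controls the general scheduling sentence and that the text already signals this. Several places support it:

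- The stage 3 and third-epinephrine bars speak of long-term maintenance, and the repeated-treatment bar of continuing long term. The protocol uses Long Term Maintenance as its heading for year 2.
- The two-epinephrine bar has no time limit.
- Build-up parameters after the 1-year challenge are to be identical to those before it.
- The build-up symptom algorithm is stated to apply both before and after that challenge.
- Footnote 5 of Appendix 1.A permits escalation and does not order it.

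Most of this stands. A reader might infer from the year-2 sentences alone that the protocol orders barred children to be re-escalated, or that nothing suggests the bar outlasts the first year. The documents support neither inference. The likely intent is that the bar governs, and a careful site would probably follow it.

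It still does not settle the matter. The Long Term Maintenance paragraph itself allows children to resume build-up in year 2. Identical parameters describe how a build-up is run, not whether one child's earlier bar carries over.

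It is also fair to say that the practical weight is limited. Escalations are supervised in clinic, the DSMB reviews after more than 3 subjects need more than one epinephrine injection for a single reaction, and stage 3 cases are mostly directed off therapy. Section 11.2 shows that some subjects may have finished before version 6.0. These facts reduce the risk, but they do not say which rule applies.

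**Conclusion.** The point holds as an unresolved conflict between two stated dosing-safety rules, and it should be fixed. It rests on the wording alone: the bars have no end date, the year-2 instructions cover everyone below 2500 mg, and no sentence reconciles them.

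The only size the documents give is the dose gap, from 350 mg (above 350 mg under the two-epinephrine bar) to 2500 mg. They do not say how many children are barred, and the practical reach depends on how many are still in year 2.

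A reader might go on to infer a bias in the sustained unresponsiveness comparison or a loss of power. Nothing in the documents supports that, and no endpoint effect is claimed.

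Nor does the point extend to children who simply fail three escalation attempts. The protocol treats them inconsistently: the initial-escalation text withdraws them, while the build-up text and the symptom algorithm keep them on the last tolerated dose. They also overlap with the repeated-treatment bar, so nothing is concluded about them here.

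**What to change.** Add this clause to the four protocol passages that direct year-2 build-up (Section 3 after the dosing table; in Section 6.4, the Egg OIT Treatment Overview, the build-up phase after the 1-year challenge, and the 1-year challenge paragraph under Both Treatment Groups): *except subjects for whom Section 6.4.2 precludes further escalation, who continue without further escalation (dose reductions and missed-dose rules still apply)*. Mirror it in footnote 5 of Appendix 1.A and, for consistency only, in SAP Section 4.1, since the SAP does not direct dosing. The parenthesis keeps the investigator's power to reduce doses and the missed-dose algorithm intact.

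Change the reference from Section 6.4.1 to 6.4.2 in the initial-escalation text of Section 6.4 and in footnote 3 of Appendix 1.A. Leave the ordinary three-attempt failures out of the clause.

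Cost: one clause in four passages and one footnote, two corrected references and one SAP sentence. Under Section 11.1 an amendment needs approval from DAIT/NIAID/NIH, the DSMB and the EC/IRB, and submission to FDA, before use. It is therefore best carried with the next amendment; the documents give no date for one. No extra visits or patients are needed. The clinical downside is that a few children stay on a lower dose in year 2.

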Those subjects still on active treatment (Baked Egg or Egg OIT) will have a 7444 mg egg white protein OFC on therapy at 2 years. Those subjects still on active therapy, but escalating doses, will discontinue escalation for 1 month prior to their 2 year 7444 mg egg white protein OFC and will be maintained on their highest tolerated dose. Those who pass the 2 year egg 7444 mg egg white protein OFC on therapy will have a repeat 7444 mg egg white protein OFC after 8-10

weeks off therapy to test for sustained unresponsiveness. If they pass this OFC off therapy (including open feeding), they will add egg to their diet and will be followed at 3 months by phone and at 6 months in clinic to assess their egg diet history and reactivity status to egg. They will be contacted annually for additional phone follow-up through September 30, 2018.

If they fail the 2 year 7444 mg egg white protein OFC on or off therapy, they will stop therapy and the study physician will review treatment options. They will also be contacted annually for additional phone follow-up through September 30, 2018.

Mechanistic Laboratory Assessments

Mechanistic labs are obtained at screening (Visit 00), 3 month (Visit 02), 6 month (Visit 03), 1 year (Visit 04), 16 months (Visit 05), 20 months (Visit 06), the 2 year visit (Visit 07), and at the 2 year sustained unresponsiveness visit (Visit 08), if applicable.

Study Design Safety Considerations

The design considers important safety issues:

- All dose escalations will be supervised in the clinic.
- The Egg OIT assignment group (that failed the baked egg challenge) will only escalate to 12 mg egg white solid maximum during the initial escalation on Day 1.
- OFC can delineate individuals who can ingest egg safely in a supervised setting.⁷⁹
- The relationship of egg-specific IgE to OFC results is unknown in individuals consuming baked egg or 350 2500 mg of egg white solid daily for up to a year. Thus, after long-term therapy, an egg OFC will be needed to determine sustained unresponsiveness irrespective of their egg-specific IgE level, and this will be performed safely in a supervised setting.

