then will return every 2 weeks to the Clinical Research Center for single dose escalation until a dose of 25 mg is achieved using the following dose escalation scheme: 3 mg to 6 mg to 12 mg to 25 mg. Subjects will be called 1 week after each dose escalation visit to assess for dosing compliance and dose reactions. Subjects should withhold their daily home dose on the escalation day but should take all other scheduled medications. Note that the daily home dose should be taken as part of a meal. It is recommended that the dose be taken at a consistent time (within a 4 hour time period), and it is critical to take the dose every day. Doses should be separated by at least 12 hours. Subjects who require dosing reduction during the 2 week period will reset their 2 week escalation schedule to maintain the new dose for a 2 week period prior to attempting to escalate again. After tolerating 25 mg egg white solid, the subject will continue dose escalations every 2 weeks. Any dose escalation attempts may be postponed for 1-2 extra weeks based on clinical judgment. An escalation attempt must be made by 4 weeks, unless escalation is delayed due to administration of epinephrine as defined in Section 6.4.1. Failure to successfully escalate for 3 consecutive attempts will result in the subject being withdrawn from further therapy. The subject will be followed for the remainder of the study for safety and immunologic monitoring. (See schedule for initial day dose escalation, Section 6, Exhibit 1) A physician will be available at all times during any of the Clinical Research Center Egg OIT dosing visits.

Any subject who discontinues escalation dosing due to repeated allergic reactions to the egg product will have his/her mechanistic blood drawn within approximately 1 week of discontinuation of therapy.

Subjects may have clear liquids and JELL-O during the day of the initial day escalation protocol while they are being given the desensitization doses.

Reactions to Egg OIT During Initial Escalation:

Process algorithm for symptoms during the initial escalation protocol. (See Section 6, Exhibit 1)

Subjects may develop symptoms during the initial escalation protocol, similar to those seen during other desensitization protocols (e.g., venom immunotherapy, drug desensitization). The investigator's judgment will be required to determine the best course of action with possible actions being the following: Extension of time interval between dosing (additional 30 minutes).

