Should significant systemic symptoms, which may include mild symptoms based on physician discretion or moderate or greater symptoms, be reported during the daily home dosing, the symptom/dosing algorithm will be followed (See Section 6, Exhibit 2) to determine the best course of action. The appropriate treatment will depend on the type and number of symptoms. If significant symptoms occur consistently following three attempts to increase the daily oral dose in the Clinical Research Center or clinic with each attempt spaced 2-4 weeks apart, dosing escalation will be halted at the last tolerated dose, the subject continued on that dose as their maintenance dose and at the scheduled 7444 mg egg white protein OFC performed at week 52. The minimally accepted dose for maintenance daily Egg OIT dosing is 350 mg egg white solid. If subjects do not reach this level by 44 weeks, Egg OIT will be discontinued and he/she will be followed until the end of the study. The maximum time allowed for the build-up phase is 44 weeks; the dose achieved at 44 weeks will be the maintenance dose used in the subsequent 8 weeks. If the subject reaches the maximum dose of OIT on or before week 44, the subject will return to the clinic for monthly assessments of dosing compliance and dosing symptoms until the 1 year OFC. The maximum length of this phase prior to the 1 year 7444 mg egg white protein OFC challenge phase is 52 weeks with the last 8 weeks prior to the year 1 desensitization OFC challenge at a constant dose.

Subjects will be allowed to take their other daily medications during the build-up and maintenance phases of the study (i.e., antihistamines, albuterol).

BUILD-UP PHASE POST 1 YEAR 7444 MG EGG WHITE PROTEIN OFC

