Starting at the maintenance dose achieved prior to the 1 year 7444 mg egg white protein OFC, subjects will begin the Clinical Research Center dosing scheme as outlined until 2500 mg of egg white solid is reached. Subjects will return for a supervised dose escalation in the clinic every 2 weeks. Subjects will be called 1 week after each dose escalation visit to assess for dosing compliance and dose reactions. Any dose escalation attempts may be postponed for 1-2 extra weeks based on clinical judgment. An escalation attempt must be made by 4 weeks. Subjects should withhold their daily home dose on the escalation day but should take all other prescribed medications. Note that the daily home dose should be taken as part of a meal. It is recommended that the dose be taken at a consistent time (within a 4 hour time period), and it is critical to take the dose every day. Doses should be separated by at least 12 hours. Subjects who require dosing reduction during the 2 week period will reset their 2 week escalation schedule to maintain the new dose for a 2 week period prior to attempting to escalate again. In year 2, when on maintenance dosing, the subject will return to the clinic every 4 months per the visit schedule with telephone contacts monthly to assess dosing compliance and any dosing symptoms.

Should significant systemic symptoms, which may include mild symptoms based on physician discretion or moderate or greater symptoms, are reported during the daily home dosing, the symptom/dosing algorithm will be followed to determine the best course of action. The appropriate treatment will depend on the type and number of symptoms. If significant symptoms occur consistently following 3 attempts to increase the daily oral dose in the Clinical Research Center or clinic with each attempt spaced 2-4 weeks apart, dosing escalation will be halted at the last tolerated dose, the subject continued on that dose as their maintenance dose. If subjects do not reach the 2500 mg maintenance dose 4 weeks prior to the end of study egg OFC, build-up will stop and the highest achieved dose will be maintained until the end of study egg OFC. Maintenance will be 4 weeks long prior to the end of study egg OFC.

Subjects will be allowed to take their other daily medications during the build-up and maintenance phases of the study (i.e., antihistamines, albuterol).

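### Three failed escalation attempts lead to withdrawal in one part of Protocol Section 6.4 and to staying on the last tolerated dose in others; for Egg OIT children at 350 mg or more this can change primary-endpoint status.

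*Protocol*

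**What the plan says.** All the rules below are in Protocol Section 6.4 and concern Egg OIT.

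- **Initial Dose Escalation.** "Failure to successfully escalate for 3 consecutive attempts will result in the subject being withdrawn from further therapy". The next sentence limits later follow-up to safety and immunologic monitoring. Three sentences before the rule, the same paragraph says: "After tolerating 25 mg egg white solid, the subject will continue dose escalations every 2 weeks".
- **Build-up before the 1-year OFC.** If significant symptoms recur over three attempts, "dosing escalation will be halted at the last tolerated dose, the subject continued on that dose as their maintenance dose". The subsection adds a floor: "The minimally accepted dose for maintenance daily Egg OIT dosing is 350 mg egg white solid". It continues: "If subjects do not reach this level by 44 weeks, Egg OIT will be discontinued".
- **Build-up after the 1-year OFC.** The trigger is "If significant symptoms occur consistently following 3 attempts to increase the daily oral dose in the Clinical Research Center or clinic", and the consequence is again to hold the last tolerated dose.
- **Symptom algorithm for build-up, before or after 1 year.** After three consecutive failed attempts, "he/she will be considered a dose escalation failure and the last tolerated dose will be accepted as the maintenance dose".

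On access to the endpoint, Protocol Section 3 (Follow-up OFCs) says: "Those subjects still on active treatment (Baked Egg or Egg OIT) will have a 7444 mg egg white" protein challenge at 2 years. SAP Section 4.1 agrees. The off-therapy challenge follows only if that one is passed (Protocol Appendix 1.A, footnote 13). SAP Section 3.3 counts a child who does not attempt the off-therapy challenge as a failure.

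**The concern.** Near-identical events have opposite consequences. One rule takes the child off therapy, so there is no on-therapy 2-year challenge, no off-therapy challenge, and a failure on the primary endpoint. The other keeps the child on a dose from which success is still possible.

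The Baked Egg arm has no escalation schedule, so any effect falls on one randomized arm only. The study is open label at five sites. If sites followed different sentences, part of the Egg OIT success rate would reflect which sentence was followed and not the treatment.

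**Working it through.** **1. Do the rules overlap?**

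| Place in Protocol 6.4 | Trigger | Consequence | Stated dose range |
|---|---|---|---|
| Initial Dose Escalation | 3 consecutive failures to escalate | Withdrawn from therapy | None; paragraph runs past 25 mg |
| Build-up, pre 1 year | Significant symptoms consistently over three attempts | Held on last tolerated dose | 350 mg floor by week 44 |
| Build-up, post 1 year | Same | Held on last tolerated dose | From the 1-year maintenance dose |
| Build-up symptom algorithm | Three consecutive failed attempts | Held on last tolerated dose | None |

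The first and last rows have essentially the same trigger and opposite outcomes. Confining the first row to the 3-to-25 mg steps does not fully separate them. Build-up starts at 12 mg for the assigned group, and the Initial Dose Escalation text also covers the step from 12 to 25 mg.

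The sentence just before the withdrawal rule cites Section 6.4.1 for epinephrine-related delays. Section 6.4.1 concerns Baked Egg reactions. The 4-week and 6-to-8-week delays are in Section 6.4.2, on build-up and maintenance.

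**2. For whom can it change the endpoint?**

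- *Stalled below 350 mg before week 44:* withdrawn at once under one rule. Under the other, held and then discontinued at week 44. Both end as a primary failure; only timing and exposure differ.
- *Last tolerated dose 350 mg or more:* withdrawn, and so a failure, under one rule. Under the other, still on treatment and able to succeed.

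**3. The plan's own figure.** Inputs from Protocol 9.3 and SAP 5: 40% vs 70%, two-sided 5%, 85% power, 96 children allocated 1:1. Protocol 2.1 gives 40% for Baked Egg and 70% for Egg OIT.

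n per arm = [1.960 × √(2 × 0.55 × 0.45) + 1.036 × √(0.4 × 0.6 + 0.7 × 0.3)]² / 0.30² = (1.379 + 0.695)² / 0.09 ≈ 47.8, so 48 per arm and 96 in total. This reproduces. Power at 48 per arm is 85.1% by this formula. Exact enumeration of the two binomials with the uncorrected chi-square test gives 85.4%.

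**4. Illustrative size.** Let f be the share of the Egg OIT arm that is withdrawn with a last tolerated dose of 350 mg or more, and s the share of those children who would have succeeded on a held dose. If the 70% presumes that they stay on dose, the rate becomes 0.70 − f × s. Neither f nor s is in the documents. For s, 27.5% is the rate in the earlier egg OIT trial (11/40, Protocol 1.1) and 70% is the design rate; both are borrowed as assumptions.

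| f (children of 48) | Rate at s = 27.5% | Exact power | Rate at s = 70% | Exact power |
|---|---|---|---|---|
| 2% (1.0) | 69.5% | 84% | 68.6% | 82% |
| 5% (2.4) | 68.6% | 82% | 66.5% | 75% |
| 10% (4.8) | 67.3% | 78% | 63.0% | 63% |
| 20% (9.6) | 64.5% | 69% | 56.0% | 36% |

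Worst case at f = 5%, s = 100%: 0.70 − 0.05 = 65%, exact power 70.3%.

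**The case against.** The strongest defence is structural. The withdrawal sentence stands under Initial Dose Escalation and is followed almost at once by a pointer to the initial-day schedule in Exhibit 1. Build-up has its own headings and points to Exhibit 2, and its three statements agree with one another. A careful reader would probably apply those during build-up. The exhibits are not in the text available for this review and might settle the scope. The algorithm also makes the Study Chair or Co-Chair available for dosing questions that the protocol leaves open, which makes uncoordinated divergence less likely. The triggers are not all worded alike; only the algorithm's closely matches the withdrawal sentence.

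Much of this stands, and it makes a narrow reading plausible. It does not remove the conflict: the sentence has no stated limit, its paragraph goes beyond 25 mg, and no precedence is given. The overlap at 12 to 25 mg in the assigned group shows that the headings do not divide the rules cleanly, although that step lies far below the floor and outside the randomized comparison.

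A reader might infer that the conflict decides endpoint status for every Egg OIT child who fails three attempts. The 350 mg floor rules that out. A reader might also infer that sites did split, or that power drops to 70% (or, with 10% of the arm withdrawn, to 51%). Nothing in the documents shows a split, and those power figures require that every withdrawn child would otherwise have succeeded.

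**Conclusion.** The contradiction is real and should be removed. Its reach is limited: it can alter primary-endpoint status only for Egg OIT children whose last tolerated dose is at least 350 mg. Below that it alters only when therapy ends and how much exposure the child has.

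The size cannot be derived from the documents. With 5% of the arm affected and 27.5% to 70% of those children otherwise succeeding, the Egg OIT rate falls from 70% to about 68.6% to 66.5%, and power from 85% to about 82% to 75%. A 65% rate with 70% power is the ceiling of harm at that share.

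These figures assume that the 70% presumes holding on dose and that the withdrawal sentence is applied to all affected children. If either fails, the loss is smaller or nil. The text conflict does not depend on these assumptions.

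**What to change.** Reconcile the three-attempt statements in Protocol Section 6.4 (Initial Dose Escalation, both build-up subsections and the build-up symptom algorithm). One consequence should apply in each phase and dose range, with that range written out. Check the result against the antihistamine and epinephrine rules in Section 6.4.2, which also provide for continuing on a dose of at least 350 mg after repeated failed attempts. Align the trigger wording, and correct the cross-reference to Section 6.4.1, since the epinephrine escalation delays are in 6.4.2. Which clinical rule should apply is for the investigators and sponsor.

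The cost is a few sentences in an amendment and a note to sites. Sample size and analysis method do not change. If dosing is already under way or complete, a listing by site of Egg OIT children with three consecutive failed attempts, their last tolerated dose and their disposition would show whether the conflict had any effect.
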